9.5 Unanticipated Problems

Definition of Unanticipated Problems (UP)

Any incident, experience, or outcome that meets all of the following criteria:

- Unexpected in terms of nature, severity, or frequency given (a) the research procedures that are described in the protocol-related documents, such as the Institutional Review Board (IRB)-approved research protocol and informed consent document; and (b) the characteristics of the participant population being studied; and

- Related or possibly related to participation in the research (“possibly related” means there is a reasonable possibility that the incident, experience, or outcome may have been caused by the procedures involved in the research); and
- Suggests that the research places participants or others (which many include research staff, family members or other individuals not directly participating in the research) at a greater risk of harm (including physical, psychological, economic, or social harm) than was previously known or expected.

Unanticipated Problem Reporting

The investigator will report unanticipated problems (UPs) to the Sponsor and Advarra. Reporting obligations and deadlines are summarized in Appendix B.

9.6 Protocol Deviations and Non-Compliance

It is the responsibility of the investigator to use continuous vigilance to identify deviations and/or non-compliance. The investigator is responsible for knowing and adhering to Advarra requirements.

Reporting obligations and deadlines are summarized in Appendix B.

Definition of Protocol Deviation and Non-compliance

A **protocol deviation** is any changed, divergence, or departure from the IRB-approved research protocol.

- Major deviations: Deviations from the IRB approved protocol that have, or may have the potential to, negatively impact the rights, welfare or safety of the subject, or to substantially negatively impact the scientific integrity or validity of the study.
- Minor deviations: Deviations that do not have the potential to negatively impact the rights, safety or welfare of subjects or others, or the scientific integrity or validity of the study.

Non-Compliance is a failure of an investigator to follow the applicable laws, regulations, or institutional policies governing the protection of human subjects in research, or the requirements or determinations of the Institutional Review Board (IRB), whether the failure is intentional or not.

10 STATISTICAL CONSIDERATIONS

10.1 Statistical Hypothesis

The objective of this protocol is to test the safety and effectiveness of the TELLTALE guidewire system in accomplishing BASILICA leaflet traversal and laceration to prevent coronary artery obstruction in the study population. The primary efficacy endpoint and the primary safety endpoint are defined in sections 4.4 and 4.5. We will use the data from this study to estimate the event rates for the primary efficacy and safety endpoints. Due to limited sample size, the study is not powered to evaluate any statistical hypotheses based on these endpoints.

10.2 Sample Size Determination

The sample size is not statistically derived.

Up to 180 candidates will be consented until 90 subjects undergo attempted TELLTALE BASILICA-TAVR in this protocol.

There is a revised quota of 30 subjects who must have native TELLTALE BASILICA-TAVR of the 90 total enrolled subjects. This is based on initial quota of 15 subjects and subsequent study expansion by 15 additional subjects with native aortic valve failure. All subjects, including the expanded native cohort, will undergo analysis for primary, secondary, and exploratory endpoints.

Rationale for Sample Size

TAVR-induced coronary obstruction is rare but devastating [1, 2]. Therefore the potential patient population is small.

The key clinically meaningful outcome is successful TAVR without coronary obstruction. We believe we are able to accomplish this using bedside-modified guidewires for BASILICA-TAVR.

It is not clear whether BASILICA increases the risk of stroke compared historically against TAVR without BASILICA. Neurological events were identified in our early prospective BASILICA IDE trial (n=30) [3, 24] but not evident in the non-adjudicated BASILICA registry (n=213) [4].

FDA CDRH reviewers transmitted the following recommendation:

We recommend increasing the size of the bioprosthetic valve subgroup to 60 subjects. This is based on a literature review of mortality and stroke rates in ViV TAVR studies that reported an average stroke rate (the lower of the two event rates) of approximately 1.4%. We suggest that the sample size be large enough to have potential to detect whether the stroke rate with TELLTALE BASILICA increases 2-fold or greater compared to clinically reported rates. For an event with anticipated incidence rate of $2 * 1.4\% = 2.8\%$, a sample size of 60 will provide $> 80\%$ probability that at least one stroke event will be observed. While we acknowledge that the study will not be hypothesis-based nor powered to detect differences in stroke/mortality, we believe these are important endpoints to consider when assessing safety and effectiveness of the BASILICA procedure with TELLTALE device, and will be incorporated into our final assessment of the totality of data. The suggested sample size of 60 provides reasonable confidence that the sample size is large enough to detect a rare event.

The bioprosthetic and native valve subgroups do not necessarily need to be balanced in size. We continue to believe that if they are not balanced, that enrollment should be weighted in favor of the bioprosthetic group, since this group appears more likely to have adverse events. As noted above, we suggest that the bioprosthetic group sample size be increased to 60. You may consider maintaining an n=15 native valve sample size, for a total sample size of n=75.

The investigators accept this recommended sample size.

In amendment B, the sample size is increased from 15 to 30 among subjects with native aortic valve failure, for a total sample size of 90.

10.3 Cohorts for Analyses

The analysis will be per-protocol, of subjects who undergo an attempt at TELLTALE BASILICA-TAVR.

Evaluable for toxicity

Complications are reflected in the primary safety endpoint, in secondary endpoints, and exploratory endpoints described in section 4 beginning on page 24.

Evaluable for objective response

Efficacy is evaluated in the primary efficacy endpoint, in secondary endpoints, and exploratory endpoints described in section 4 beginning on page 24.

10.4 Statistical Analyses

Exploratory data analysis will assess for missing values and will generate data clarification requests as required. We expect few missing data. If there are missing data to evaluate the primary efficacy endpoint or primary safety endpoint for a study subject, the endpoint with missing information will be considered a failure for the applicable subject. The primary analysis will be based on the intention-to-treat (ITT) population that includes all study subjects. We will also perform an as-treated analysis in a sensitivity analysis.

For the primary efficacy endpoint, primary safety endpoint and secondary endpoint, we will estimate the event rate by the sample proportion of subject who meet the given endpoint with 95% confidence interval. Descriptive statistics will be used to summarize the baseline demographic characteristics, subject and procedure characteristics, and the exploratory endpoints. For continuous variables, the mean (standard deviation) or median (interquartile range) will be presented. For categorical variables, the frequency and the percentage in each category will be presented. Exploratory post-hoc analyses will be performed as unusual observations and novel questions arise, including those requiring additional data abstraction from the source documents or images.

In an exploratory analysis, results including the primary efficacy endpoint for device technical success and 30-day VARC3 safety will be compared with those outcomes from a previously completed study, the NHLBI BASILICA IDE protocol (NCT03381989) of bedside-modified traversal and laceration guidewires. Fisher's exact tests will be used to compare these outcomes between two studies.

The key study results (primary and secondary endpoints) will be analyzed by subgroups including indication (bioprosthetic versus native), site, census region, age (dichotomized by the sample median), non-white status, and sex. For each of the above baseline characteristics, the subgroup differences in the study outcome will be evaluated by the two-sided Fisher's exact test at a significance level of 0.05. For the subgroup analysis of study sites, the sites with smallest number of patients will be combined to have at least 5 subjects in the pseudo-site group.

Statistical analysis will be performed or confirmed by the NHLBI study statistician.

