The prospective FDA IDE NHLBI BASILICA study enrolled 30 patients at high risk of coronary artery obstruction from TAVR who underwent BASILICA with an Astate guidewire with benchtop modification[3]. All patients were at high risk of coronary obstruction as determined by the NHLBI CT core laboratory. Seven (23%) were double-leaflet BASILICA. Primary success of successful BASILICA and TAVR without coronary obstruction or reintervention was met in 28 (93%) subjects. BASILICA traversal and laceration was successful in 28 (93%) subjects. There was 100% freedom from coronary obstruction and reintervention. Primary safety of freedom from MACE was met in 21 (70%), driven by six (20%) major vascular complications related to TAVR but not BASILICA. There was one death at 30 days. There was one (3%) disabling stroke and two (7%) non-disabling strokes. Transient hemodynamic compromise was rare (7%) and resolved promptly with TAVR. At one year, there were no late complications associated with BASILICA[24]. Specifically, after 30 days there was no stroke, myocardial infarction, coronary intervention, transcatheter aortic valve failure or increase in valve gradients. The coronaries remained clinically patent and there were no BASILICA related deaths.

The international multicenter BASILICA Registry reported results on 214 patients undergoing BASILICA and TAVR in patients at high risk of coronary artery obstruction[4]. 22% were *doppio* (double-leaflet) BASILICA. Procedural success, a composite of successful traversal and laceration, survival and freedom from coronary obstruction or re-intervention was seen in 87%. The 30-day mortality was 2.8% and stroke rate 2.8% (0.5% disabling stroke).

The EURO-BASILICA multicenter registry reported 76 patients at 10 centers undergoing BASILICA and TAVR in patients at high risk of coronary artery obstruction, using commercial off-the-shelf devices [25]. Nine (12%) were *doppio* (double-leaflet) BASILICA. Technical success was 98%, freedom from coronary obstruction was 91%, stroke was 3%. Ten patients required coronary intervention, typically because of avulsed or prolapsed leaflets amenable to orthotopic stenting.

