An interim analysis of this open-label study for amendment B (September 2023) was triggered by consent of 15 subjects with native aortic valve failure. At this timepoint 27 subjects were treated by TELLTALE BASILICA TAVR, including 14 with native aortic valve failure. Using non-adjudicated data, the primary success rate is 100%, the incidence of coronary obstruction is 0%, and the incidence of stroke/TIA is 0%. Based on these data we propose amending the protocol in Amendment B to expand the study cohort having native aortic valve failure, from 15 to 30 subjects.

These studies provide reassuring data in support of the BASILICA procedure to prevent coronary artery obstruction in this patient cohort with few good options.

Available literature about risks of coronary obstruction

Reported and expected outcomes of patients undergoing TAVR despite risk of coronary obstruction

Setting	n with CTs evaluated	At-risk population	Cor obstruction in at-risk population	30-day Death	Stroke	Reference
ViV	20 obstructed, 90 control	VTC<4mm	89%	53% (in obstructed population)	0%	VIVID registry [2]
Native AS	28 obstructed, 345 control	coronary height<12mm and SOV width <30mm	87%	41% (in obstructed population)	9%	Multicenter Registry [1]
Native AS	60 obstructed, 60 control	Leaflet height ≥ coronary height AND VTC<4mm	90%	27% (in-hospital death, obstructed)	Not collected	CRT 2020 late breaking trial presentation, not published
VIV and Native	30 attempted BASILICA	Leaflet height ≥ coronary height AND VTC<4mm; Leaflet height ≥ STJ AND VTSTJ<2mm	0%	3%	10%	[3]
VIV and Native	214 attempted BASILICA	Leaflet height ≥ coronary height AND VTC<4mm; Leaflet height ≥ STJ AND VTSTJ<2mm	5%	3%	3%	[4]
VIV and Native	15 attempted BASILICA	Leaflet height ≥ coronary height AND VTC<4mm; Leaflet height ≥ STJ AND VTSTJ<2mm	7%	0%	0%	[26]
VIV and Native	21 attempted BASILICA	Leaflet height ≥ coronary height AND VTC<4mm; Leaflet height ≥ STJ AND VTSTJ<2mm	5%	0%	0%	[27]

Compared with pivotal trials in which all candidates at risk of coronary obstruction are EXCLUDED

Setting	Population	n	Cor obstruction	30-day Death	Stroke	
Native AS	Excluded "Bulky calcified aortic valve leaflets in close proximity to coronary ostia"	348	0%	3.4%	3.8%	PARTNER 1
Native AS	Excluded "Bulky calcified aortic valve leaflets in close proximity to coronary ostia"	1011	0.4%	3.9%	5.5%	PARTNER 2
Native AS	Excluded "Bulky calcified aortic valve leaflets in close proximity to coronary ostia"	496	0.2%	0.4%	0.6%	PARTNER 3

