6.2 Exclusion Criteria

- Requires doppio (two-leaflet) BASILICA
- Flail target leaflet at baseline
- Excessive target aortic leaflet calcification (no basal calcium-free window or potentially obstructive calcific masses) on baseline CT
- Planned provisional (pre-position coronary artery) stents despite BASILICA
- Requires non-femoral access
- Requires concomitant procedures during TAVR (such as percutaneous coronary intervention for baseline obstructive coronary artery disease)
- Chronic kidney disease KDIGO stage 4 or 5 (eGFR < 29 ml/min/1.73m²) or renal replacement therapy
- Not expected to survive for 12 months
- Pregnant at the time of intended treatment (day 0)

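### The exploratory comparison with the 30-subject BASILICA IDE study would be better reported as a difference with an interval, with a single-leaflet sensitivity comparison beside the Fisher tests (minor, cheap improvement)

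*Combined protocol and SAP*

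**What the plan says.** Section 10.4 plans two separate things. Within this trial, for the primary and secondary endpoints, "we will estimate the event rate by the sample proportion of subject who meet the given endpoint with 95% confidence interval". Against the completed NHLBI BASILICA IDE study of bedside-modified guidewires, it plans an exploratory comparison of results that include device technical success and 30-day VARC-3 safety. For that comparison the only method named is Fisher's "exact tests will be used to compare these outcomes between two studies". No difference, ratio or interval between the studies is mentioned, and no subset of the IDE study is specified. The two-sided Fisher's "exact test at a significance level of 0.05" is specified for the subgroup analyses; neither sidedness nor level is given for the between-study tests.

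Section 10.1 says that the data will be used to estimate event rates and that "the study is not powered to evaluate any statistical hypotheses based on these endpoints".

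Section 3.2 describes the comparator: 30 subjects, of whom "Seven (23%) were double-leaflet BASILICA", and "BASILICA traversal and laceration was successful in 28 (93%) subjects". Section 6.2 excludes a candidate who "Requires doppio (two-leaflet) BASILICA". Section 6.4 explains that discordant results in the two leaflets would affect how the primary efficacy endpoint is assessed.

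**The concern.** This is the plan's comparison of the purpose-built wire with bedside-modified wires. Section 3.3 expects the new system to be non-inferior to them, and section 5.3 calls it intrinsically superior. A Fisher p-value against 30 subjects informs neither statement well. A large p-value is easily misread as similarity, and it does not show how large a deficit or gain the data leave open.

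The second issue is like-for-like comparison. By the protocol's own reasoning, two-leaflet cases complicate the scoring of technical success, which is one of the outcomes compared. Yet 23% of the comparator is of that type, and the plan does not say whether those subjects stay in. If the comparator is settled after the results are known, the choice could look convenient. A near-perfect result is a realistic prospect: at the Amendment B interim look, with 27 subjects treated, section 3.2 reports "Using non-adjudicated data, the primary success rate is 100" per cent.

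**Working it through.** **Inputs from the documents.** IDE study (section 3.2): 30 subjects, 7 two-leaflet, 28 with successful traversal and laceration. This trial: 90 subjects (section 10.2).

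**Assumptions.** Illustrative TELLTALE counts out of 90; 28/30 as the IDE technical success count; Fisher two-sided; Newcombe 95% intervals. No safety figure is worked, because the documents give no IDE count labelled VARC-3.

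**The plan's own figures.** 7/30 = 23.3% and 28/30 = 93.3%, as stated. That leaves 30 − 7 = 23 single-leaflet subjects and 30 − 28 = 2 failures.

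**Fisher, 90/90 vs 28/30.** There are 2 failures among 120 subjects, both in the IDE group: C(30,2)/C(120,2) = 435/7140 = 0.061. The other possible tables are more probable, so this is also the two-sided p-value. A perfect result therefore cannot reach two-sided 0.05 against the full IDE group.

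**Newcombe interval.** With Wilson limits (l, u) for each proportion and d = p1 − p2:
- lower = d − √[(p1 − l1)² + (u2 − p2)²]
- upper = d + √[(u1 − p1)² + (p2 − l2)²]

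For 84/90 vs 28/30, the Wilson limits are 86.21 to 96.91 and 78.68 to 98.15, both around 93.33, so d = 0:
- lower = −√(7.12² + 4.82²) = −8.6
- upper = √(3.58² + 14.65²) = 15.1

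| Assumed TELLTALE vs IDE 28/30 | Fisher p | Difference, points (95% CI) |
|---|---|---|
| 90/90 | 0.061 | +6.7 (0.3 to 21.3) |
| 89/90 | 0.154 | +5.6 (−1.3 to 20.2) |
| 84/90 | 1.0 | 0.0 (−8.6 to 15.1) |
| 80/90 | 0.728 | −4.4 (−13.9 to 11.0) |

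In the first row the interval excludes zero while p exceeds 0.05, so the two summaries can disagree at the boundary.

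**Single-leaflet comparator.** The documents do not say which subjects the 2 IDE failures were. If 2, 1 or 0 of them were single-leaflet, the comparator is 21/23, 22/23 or 23/23. For 90/90 the p-values are C(23,2)/C(113,2) = 253/6328 = 0.040, then 23/113 = 0.20, then 1.0.

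| Assumed TELLTALE vs single-leaflet IDE | Fisher p | Difference, points (95% CI) | CI width |
|---|---|---|---|
| 90/90 vs 21/23 | 0.040 | +8.7 (1.2 to 26.8) | 25.6 |
| 90/90 vs 22/23 | 0.20 | +4.3 (−1.1 to 21.0) | 22.1 |
| 90/90 vs 23/23 | 1.0 | 0.0 (−4.1 to 14.3) | 18.4 |
| 89/90 vs 21/23 | 0.105 | +7.6 (−0.4 to 25.7) | 26.1 |

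The width for 90/90 against the full 28/30 is 21.0 points. Towards superiority, restriction crosses 0.05 only when the result is 90/90 and both IDE failures were single-leaflet.

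**Definition of success.** Section 4.4 requires traversal, laceration and retrieval of the guidewire. Section 3.2 states the 28/30 as traversal and laceration only. Every comparison above takes 28/30 as equivalent, which the documents do not confirm.

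**The case against.** The strongest reply is that little hangs on this. The comparison is labelled exploratory, the study is declared unpowered, and no success criterion uses the result. That stands, and it sets the weight of the point.

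A second reply is that the information is already there. This trial's proportions come with intervals and the IDE efficacy count is in section 3.2, so a reader can form the difference. That is true of the direction and the crude difference. What is missing is a prespecified between-study interval and its method. The method matters at the boundary: for 89/90 vs 21/23 the lower limit is −0.4 points by Newcombe and +0.2 by Miettinen-Nurminen.

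A third reply is that section 10.4 permits post-hoc exploratory analyses, so the restricted comparison could be run anyway. It could, but choosing it afterwards is weaker than naming it now.

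A reader might infer that the two-leaflet subjects bias the comparison, for instance by lowering the IDE success rate and flattering the new wire. The documents do not support that. They report neither whether any of the seven had discordant leaflet results nor how the two failures split by leaflet type. It would also be wrong to present the 0.040-to-1.0 spread as typical: it belongs to a perfect 90/90.

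**Conclusion.** The point holds as a minor, low-cost improvement. Section 10.4 plans a test alone where an estimate with an interval would say more and would fit the estimation aim of section 10.1. With 30 historical subjects, p=1.0 is compatible with anything from 8.6 points worse to 15.1 points better. The comparator includes 7 of 30 subjects of a type this trial excludes, and the plan does not say how they are handled. No bias is shown, its direction is unknown, and the effect of restriction on the p-value is limited, as the 89/90 result shows.

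A reader might also infer that the trial's conclusions are at risk, or that the inability of 90/90 to reach significance is a design failure. Neither follows: the primary analyses are single-arm estimates, and the protocol claims no power for this comparison.

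The sizes rest on assumed TELLTALE counts, 28/30 as the IDE figure, two-sided Fisher tests and Newcombe intervals.

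**What to change.** In section 10.4:

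- **(a)** For both outcomes, make the between-study difference in proportions with a Newcombe 95% confidence interval the lead summary. Keep the Fisher p-value as supporting only, and state its sidedness. Saying which one leads settles boundary cases such as 90/90 vs 28/30 in advance.
- **(b)** Prespecify a sensitivity comparison with the 23 single-leaflet IDE subjects, reported beside the full 30.
- **(c)** Score IDE technical success by section 4.4, including guidewire retrieval, where the IDE records allow. Say so where they do not.

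The cost is a few lines of text and a reanalysis of existing IDE data; section 3.2 shows that leaflet type was recorded. Item (c) may need some record review. Enrolment, endpoints and primary analyses are unchanged. The downside is that the restricted comparator is smaller and its interval usually wider (in two of the three 90/90 cases above). It removes only one known case-mix difference. Other historical-control differences and low power remain, which is why the full cohort should stay alongside.

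### Section 10.4 tests age only as a sample-median split with Fisher's exact test, which wastes about a quarter to a third of the age information and can barely reject when failures are few

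*Combined protocol and SAP*

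**What the plan says.** Section 10.4 (Statistical Analyses) states that "The key study results (primary and secondary endpoints) will be analyzed by subgroups". The listed factors are indication, site, census region, "age (dichotomized by the sample median), non-white status, and sex". For each one, "the subgroup differences in the study outcome will be evaluated by the two-sided Fisher's exact test at a significance level of 0.05". Age is the only continuous factor on the list. The section gives no reason for the cut, no rule for ages equal to the median, no analysis of age as a continuous variable and no minimum number of failures.

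Three other statements bear on the point. Section 10.2 sets the numbers, "for a total sample size of 90". Section 10.1 says that "the study is not powered to evaluate any statistical hypotheses based on these endpoints". On missing primary-endpoint data, section 10.4 says that "the endpoint with missing information will be considered a failure for the applicable subject", which can raise the failure count.

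**The concern.** Age is recorded for every subject, and the split throws away everything except which side of the median a subject falls on. The cut-point is set by whoever happens to be enrolled and carries no clinical meaning. When an endpoint has very few failures, Fisher's test on two groups of about 45 has only a handful of possible p-values, and the smallest may lie above 0.05.

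What is at stake is interpretation. A non-significant age result could be taken to mean that the device performs alike in younger and older patients, when the test had little or no chance of showing otherwise. This is a separate matter from the multiplicity of the subgroup tests.

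**Working it through.** The plan states no power or detectable difference for the age test, so there is no figure of its own to reproduce on this point. The one sample-size probability in section 10.2 does check: 1 − (1 − 0.028)^60 = 0.818, in line with the claim of more than 80%.

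**Inputs.** From the documents: N = 90, two-sided Fisher test at 0.05 (sections 10.2 and 10.4). From section 3.2: "BASILICA traversal and laceration was successful in 28 (93%) subjects" in the earlier IDE study of 30, so 90 × 2/30 = 6 failures; 100% primary success in 27 treated subjects at this study's non-adjudicated interim look, so no failures; freedom from MACE in 21 of 30 in the earlier study, so 90 × 9/30 = 27 failures. The earlier study's endpoints and case mix differ somewhat from this one's, so these counts are guides only. Assumed, because the documents do not give them: the age distribution, the size and shape of any age effect, and the final failure counts.

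**1. Smallest attainable p, equal halves.** With 45/45 and all f failures in one half, p = 2·C(45,f)/C(90,f).

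| Failures | Minimum two-sided p |
|---|---|
| 2 | 0.494 |
| 3 | 0.242 |
| 4 | 0.117 |
| 5 | 0.0556 |
| 6 | 0.0262 |

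Five or fewer cannot reach 0.05; six can, but only if all six fall in the same half.

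**2. Unequal halves.** At 44/46 with five failures:
- all in the smaller group: C(44,5)/C(90,5) = 0.0247
- all in the larger group: [C(46,5) + C(44,5)]/C(90,5) = 0.0559

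At 43/47 with four failures the corresponding values are 0.0483 and 0.118. So whether significance is attainable depends on the side on which the failures fall. If ages tie at the median, it also depends on whether subjects at the median are put in the upper or the lower group. With ages in whole years (assumed SD 8), an exact 45/45 split arose in only about 22% of simulated trials, and the larger group was typically 47.

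**3. How likely five or fewer failures are.** Binomial, n = 90:

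| True failure rate | P(5 or fewer) |
|---|---|
| 2% | 0.99 |
| 5% | 0.70 |
| 6.7% | 0.44 |
| 10% | 0.10 |
| 30% | about 0 |

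**4. Information kept by the split.** Asymptotic efficiency of a median split against a linear trend is 2/π = 64% for normally distributed age and 75% for uniform age, a loss of 36% and 25%.

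**5. Power.** Simulated with n = 90, whole-year ages (mean 80, SD 8) and an odds ratio of 2.0 per SD:

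| Failure rate | Split, Fisher | Continuous age, rank-sum |
|---|---|---|
| 5% | about 11% | about 25% |
| 10% | about 23% | about 42% |
| 30% | about 56% | about 78% |

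With no age effect, the rank-sum test rejected in 4–5% of trials and the split test in 1.4–4.0%. The gain therefore does not come from an inflated error rate; part of it is Fisher's unused alpha. If risk instead steps up or down at the middle of the age range, the two tests are about equal, within some four percentage points at each failure rate when the upper group is taken as strictly above the median.

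**6. Floor after the change.** An exact rank test on untied ages has minimum p = 2/C(90,f): 0.022 with one failure, 0.0005 with two. The floor disappears.

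**The case against.** The strongest reply is that the plan already limits what these tests can show. Section 10.1 disclaims power for any hypothesis on the primary endpoints, the aim is estimation, and section 10.4 allows post-hoc exploratory analyses, so continuous age is not barred. The median rule is prespecified and matches the layout of the other subgroups. All of that is true, but section 10.4 still prescribes a 0.05 test by age, and a small study has the more reason not to waste information it already holds.

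A second reply is that the better test does not make a null result informative: about 25% power at 5% failures is still poor, and with no failures no test of age works. This stands, and it is why the fix needs an interpretive caution as well as a new test. It also stands that the advantage depends on the shape of the effect; with a mid-range step there is essentially none.

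A reader might infer that the split discards most of the information. It does not: the split alone costs 25% to 36%, and the rest of the power gap at low counts comes from Fisher's conservatism. A reader might also infer that five or fewer failures can never give p<0.05. That is so only for exactly equal halves, as the 44/46 case shows.

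**Conclusion.** The point holds as a modest improvement to a secondary part of the analysis. On a linear age trend the planned test has roughly half the power of a rank-sum test at a 5% failure rate, and clearly less even at 30%. These figures rest on the assumed age distribution and odds ratio.

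The floor on p matters mainly for primary efficacy, where counts near or below five are plausible. It is immaterial for the 30-day endpoint if failures run near the 27 implied by the earlier study; there only the information loss applies. The documents do not support extending the concern to the study's main results: the primary and secondary rates, their confidence intervals, the sample size and the stopping guidance are untouched. Nor do they say that a null subgroup test will be read as equivalence; that is a risk of interpretation which the plan leaves open.

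**What to change.** In section 10.4:
- Test age on its continuous scale with the exact Wilcoxon rank-sum test, comparing subjects who do and do not meet each endpoint, and report the odds ratio per 10 years with a 95% CI from exact or Firth logistic regression.
- Keep the rates below and above the median as a descriptive table only, and state in advance which group takes ages equal to the median.
- Keep Fisher's test for the categorical factors.
- State that a non-significant age result is not evidence of no difference by age.

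This costs a few sentences and one extra analysis step, with no new data. The small downside is that an odds ratio per 10 years is slightly harder to read than two rates, which is the reason to keep the table.
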